# 6.12.8. Electrocardiograms

Results of electrocardiograms (ECGs) performed during the study will not be reported.

# 6.12.9. Immunogenicity

If data from validated immunogenicity assays are available, treatment-emergent antidrug antibodies (TE-ADAs) may be assessed.

Treatment-emergent ADAs are defined as participants

with a 2-fold (1 dilution) increase in titer compared with the minimum required dilution if no antidrug antibodies (ADAs) were detected at baseline (treatment-induced ADA) or

with a 4-fold (2 dilutions) increase in titer compared with baseline if ADAs were detected at baseline (treatment-boosted ADA).

The frequency and percentage of participants with preexisting ADAs and who are TE-ADA positive (TE-ADA+) to LY3819253 and/or LY3832479 may be tabulated.

The distribution of titers and frequency of neutralizing antibodies (if assessed) for the TE-ADA+ participants may also be tabulated.

The relationship between the presence of antibodies and PK parameters, efficacy response, or safety to LY3819253 and/or LY3832479 may also be assessed.

<sup>aThe high limit values shown in this table correspond to 95th percentile for the age group under the 2017 ACC/AHA Task Force on Clinical Practice Guidelines revised criteria for hypertension. Values higher than 95th percentile are consistent with Stage 1 or Stage 2 hypertension. Under some circumstances it may be appropriate to conduct analyses considering only the change from baseline reference limit.

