2.4. Section 4.0. Study Design

This addendum adds a single open-label treatment arm (Arm 23) to evaluate bebtelovimab administered as an intravenous injection to pediatric participants.

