2.12. Section 10.6. Appendix 6: Recommended Laboratory Testing for Hypersensitivity Events

Purpose of collecting samples after a systemic hypersensitivity event

The samples listed in this appendix are not collected for acute study participant management. The sponsor will use the laboratory tests results from these samples to characterize hypersensitivity events across the clinical development program.

When to collect samples after a systemic hypersensitivity event occurs

Collect the samples listed below if a systemic hypersensitivity event is suspected. The timing should be as designated in the table, assuming the participant has been stabilized.

Obtain follow-up pre-dose samples at the next regularly scheduled laboratory sample collection (ideally prior to the next dose after the event) to assess post-event return-to-baseline values.

Timing	Sample Type	Laboratory Test ^a
Collect from 30 minutes to 4 hours after the start of the event. 
 Note: The optimal collection time is from 1 to 2 hours after the start of event. 	Serum	total tryptase
	Serum	complements (C3, C3a, and C5a)
	Serum	cytokine panel (IL-6, IL-1 β , IL-10 or any cytokine panel that includes these 3 cytokines)
Collect only if not already collected on the same day as the event. 
 Note: If collecting, collect up to 12 hours after the start of the event. 	Serum	Bebtelovimab anti-drug antibodies (ADA)
	Serum	Bebtelovimab concentration

^a All samples for hypersensitivity testing will be assayed by Lilly-designated laboratory. Results will not be provided to the study site. If samples are not collected or are collected outside the specified time period, this will not be considered a protocol deviation.

Abbreviations: ADA = anti-drug antibodies; IL = interleukin.

What information to record

Record the date and time when the samples are collected.

Allowed additional testing for participant management

The investigator may perform additional tests locally, if clinically indicated, for acute study participant management.

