### LY3853113 - Mild to Moderate COVID-19 Illness

This addendum is a Phase 2, single-arm, open label, uncontrolled, single-dose study in participants with mild to moderate COVID-19 illness to evaluate the pharmacokinetics and safety of bebtelovimab (LY3853113) in the pediatric population.

Eli Lilly and Company Indianapolis, Indiana USA 46285 Protocol J2W-MC-PYAB Phase 2/3

Supplemental Statistical Analysis Plan Version 1 electronically signed and approved by Lilly on date provided below.

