# 6.11. Bioanalytical and Pharmacokinetic/Pharmacodynamic Methods

Pharmacokinetic and PD analyses are the responsibility of the Eli Lilly and Company PK/PD group.

Bebtelovimab concentration data will be analyzed using a population PK approach via nonlinear mixed-effects modeling with the NONMEM software. In addition, the effects of participant factors, such as weight and age on PK parameters may be evaluated. If antidrug antibody is detected from immunogenicity testing, its impact on bebtelovimab PK may also be evaluated.

A limited number of pre-identified individuals may gain access to interim data prior to the primary lock, in order to initiate the population PK/PD model development processes.

Pharmacodynamic endpoints will be summarized using descriptive methodology. The SARS-CoV-2 viral dynamics will include evaluation of

change from baseline in SARS-CoV-2 viral load (Days 5, 7, and 11) AUC, and time to SARS-CoV-2 clearance.

Additional PK/PD concentration-response analysis may be performed PK/PD analyses on adolescents in the study will be treated as secondary to support the pediatric analyses.

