# 6.12. Safety Analyses

Percentages will be calculated using the safety population as the denominator. For events that are sex-specific, the denominator and computation of the percentage will include only participants from the given sex.

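### SAP 6.12.9 specifies its antibody outputs for two products that Arm 23 does not give, and sets no denominator that leaves out participants under 12 kg, who have no ADA samples

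*SAP*

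**What the plan says.** The SAP's title text says that the addendum is there to "evaluate the pharmacokinetics and safety of bebtelovimab (LY3853113) in the pediatric population". Protocol addendum 2.4 agrees: "This addendum adds a single open-label treatment arm (Arm 23) to evaluate bebtelovimab administered as an intravenous injection to pediatric participants".

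SAP 6.12.9 contains two sentences that name an antibody target, and both are optional. The first covers participants with preexisting ADA and those "TE-ADA positive (TE-ADA+) to LY3819253 and/or LY3832479 may be tabulated". The second covers the relationship of antibodies with PK parameters, "efficacy response, or safety to LY3819253 and/or LY3832479 may also be assessed". LY3853113 does not appear in the section.

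On the denominator, the opening of SAP 6.12 says: "Percentages will be calculated using the safety population as the denominator". The only exception given there is for sex-specific events. SAP 6.1.1 defines the safety population by receipt of any amount of study drug. The protocol's Appendix 10 (addendum 2.14) and the ADA row of its Schedule of Activities (addendum 2.2.1) both state that participants under 12 kg have no ADA samples. The Schedule also waives the sample for a hospitalized participant.

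**The concern.** There are two separate faults, and repairing one leaves the other in place.

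First, an output programmed from 6.12.9 as written would be specified for antibodies to products that nobody in this cohort receives. The bebtelovimab table, and the bebtelovimab antibody-efficacy and antibody-safety assessments, would have no specification.

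Second, if only the codes are corrected, the percentages still inherit the safety-population denominator. Participants who were never sampled by design would be counted as though they had been tested and found not positive, so both ADA percentages would be too low. The missing data follow body weight, which also defines the dosing groups and an analysis stratum in SAP 5.3. The effect is therefore concentrated in the smallest children, where a reader could take not sampled to mean no immunogenicity.

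**Working it through.** The plan states no figure on this point, so there is none to reproduce. The check is a comparison of texts followed by simple arithmetic.

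**Product**

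| Place | Product named |
|---|---|
| Protocol addendum 2.4 and 2.8 (Arm 23) | bebtelovimab, LY3853113 |
| SAP title text | bebtelovimab, LY3853113 |
| Protocol Appendix 6 (addendum 2.12), ADA test | bebtelovimab |
| SAP 6.11, effect of ADA on PK | bebtelovimab |
| SAP 6.12.9, preexisting-ADA and TE-ADA table | LY3819253 and/or LY3832479 |
| SAP 6.12.9, antibody relationships | LY3819253 and/or LY3832479 |

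Both target-naming sentences in 6.12.9 disagree with every other entry. For PK the gap is closed elsewhere, since SAP 6.11 says: "If antidrug antibody is detected from immunogenicity testing, its impact on bebtelovimab PK may also be evaluated". For the table and for the efficacy and safety relationships, nothing else in the SAP closes it.

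**Denominator**

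1. The lower weight limit for entry is 3.3 kg (protocol addendum 2.7.1), so participants under 12 kg can be enrolled and dosed. They are then in the safety population.
2. They have no ADA samples. TE-ADA in 6.12.9 is a titer increase judged against baseline status, and preexisting ADA needs a baseline result. Neither can be determined for them.
3. SAP 6.12.9 states no denominator of its own, so the 6.12 default applies. By contrast, the shift tables in SAP 6.12.7 do state theirs.

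Let N be the safety population, k the number not evaluable for the percentage, and p the true rate among evaluable participants. Then

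reported % = p × (N − k)/N, and relative understatement = k/N, whatever p is.

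N = 50 is the planned size. N = 70 adds the approximately 20 adolescents that SAP 5.3 allows (50 + 20). The values of k and p = 10% are assumptions. The minimum of 5 participants aged 0 to <2 years does not fix k, because it is set by age and not by weight.

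| | k = 1 | k = 5 | k = 10 | k = 20 |
|---|---|---|---|---|
| N = 50, factor (N − k)/N | 0.98 | 0.90 | 0.80 | 0.60 |
| N = 50, 10% reported as | 9.8% | 9.0% | 8.0% | 6.0% |
| N = 70, factor (N − k)/N | 0.986 | 0.929 | 0.857 | 0.714 |
| N = 70, 10% reported as | 9.9% | 9.3% | 8.6% | 7.1% |

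For example, with N = 50 and k = 5: 10% × (50 − 5)/50 = 9.0%.

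**Weight row**

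One result needs no assumed k. The lowest category in SAP 5.3 runs from 3.3 kg up to and including 12 kg, and ADA sampling is omitted below 12 kg. Within that row only a participant of exactly 12 kg has scheduled ADA samples. So (n − k)/n is about 0, and the row would read about 0% for any true rate.

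**Hospitalized participants**

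The ADA schedule is Day 1 before dosing, then Days 11, 29 and 60 and early discontinuation. Read visit by visit, the waiver removes a participant from the preexisting-ADA percentage only if the Day 1 sample is missing. It removes a participant from the TE-ADA percentage only if the Day 1 sample or every post-baseline sample is missing.

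**The case against.** The strongest reply on the codes is that they are carried-over text. Both belong to the parent study title printed in the SAP's table of contents. The opening sentence of 6.12.9 and its TE-ADA definition name no product, and everything around the section points to bebtelovimab. That is a fair account of how the error arose, and an analyst may well notice it. But these are the sentences that specify the outputs, and for the table and the efficacy and safety relationships no other text corrects them.

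On the denominator, SAP 6.1.4 excludes participants without a valid baseline from change-from-baseline analyses, and SAP 6.1.2 sets a change to missing when either value is missing. One could read TE-ADA as such an analysis. One could also read the 6.12 rule as aimed at event percentages, since its next sentence speaks of events. These readings are possible, but neither clearly overrides a rule stated for percentages in general, and the change-from-baseline provisions cannot reach the preexisting-ADA percentage, which involves no change. It does stand that the SAP nowhere says outright that unsampled participants count as negative; that follows from applying the default.

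A reader might infer that all hospitalized participants are unclassifiable too. The documents do not support that. Day 1 is an outpatient clinic visit with a pre-dose sample, so someone admitted later normally has a baseline sample and further ADA visits. Hospitalization for reasons other than COVID-19 is compatible with entry (exclusion criterion 32), so a missing baseline sample is possible, but it is not the general case.

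**Conclusion.** Wrong as written, with minor impact. The product error is certain: both target-naming sentences in 6.12.9 name products outside Arm 23. The denominator fault holds for participants under 12 kg under the SAP 6.12 default, and for hospitalized participants only where the waiver leaves no baseline sample or no post-baseline sample.

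The overall size of the dilution is not known. It equals k/N, and the documents give neither k nor an expected ADA rate, so the table of reported percentages is illustrative only. The near-zero lowest weight row depends on no assumed rate or count, but it arises only if the optional table is produced, is split by dosing weight and uses the default denominator.

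A reader might also infer harm to the main results. The documents do not support that: every output in 6.12.9 is optional, immunogenicity is not a listed objective or endpoint, and the primary AUC analysis uses neither these codes nor this denominator.

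**What to change.** In SAP 6.12.9:

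- Replace the two product codes with LY3853113 (bebtelovimab) in both sentences. This also settles which product the PK clause of the second sentence refers to.
- State, as an exception to SAP 6.12, that the preexisting-ADA percentage uses participants with an evaluable baseline ADA sample, and that the TE-ADA percentage uses participants with an evaluable baseline and at least one evaluable post-baseline ADA sample.
- Report the number of participants not evaluable, and show any weight row with no evaluable participant as not assessed.

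The cost is two phrase replacements, one denominator statement and one reporting rule in the SAP. No sample, visit or trial procedure changes.

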# 6.13. Subgroup Analyses

This study is not powered for subgroup analyses; therefore, all subgroup analyses will be treated as exploratory.

Subgroup analyses will be conducted for the primary endpoint. Subgroups may include

```
time from symptom onset to study treatment
baseline severity of COVID-19
age group (<2, 2 to <6, 6 to <12, 12 years and older)
gender (male, female)
race
ethnicity
baseline weight (≥3.3 to ≤12 kg, >12 to ≤20 kg, >20 to <40 kg, ≥40 kg)
concomitant medication of interest use (yes/no)
```

The analysis of additional subgroups and/or subgroup analyses on additional endpoints will not require an amendment to the SAP.

Concomitant therapies of interest include remdesivir, lopinavir/ritonavir, chloroquine, hydroxychloroquine, anticoagulants, dexamethasone, or other investigational interventions. Details of the medications included in this subgroup are provided below in Table PYAB.6.11.

Table PYAB.6.11. Concomitant Medications of Interest Subgroup

Drug name	ATC Code	Who Drug Preferred Term	
Remdesivir		REMDESIVIR	
Kaletra	J05AR	KALETRA	
Lopinavir	J05AR	LOPINAVIR	
Hydroxychloroquine	P01BA	HYDROXYCHLOROQUINE	
Chloroquine	P01BA	CHLOROQUINE	
Baricitinib	L04AA	BARICITINIB	
Heparin	B01AB	HEPARIN	
Fondaparinux	B01AX	FONDAPARINUX	
Argatroban	B01AE	ARGATROBAN	
Dexamethasone	H02AB	DEXAMETHASONE	

Abbreviation: ATC = anatomical therapeutic chemical.

### 6.14. Protocol Violations

Protocol deviations will be identified throughout the study. Important protocol deviations (IPDs) are defined as those deviations from the protocol that would potentially compromise participants' safety, data integrity, or study outcome.

A separate document known as the "PYAB Trial Issues Management Plan" describes the categories and subcategories of IPDs and how the IPDs would be identified.

The number and percentage of participants having IPDs will be summarized within category and subcategory of deviations by dosing regimen.

A by-patient listing of IPDs will be provided.

# 6.15. Interim Analyses and Data Monitoring

# 6.15.1. Interim Analyses

No formal interim analyses are planned for this cohort.

### Unblinding

This is an open-label, single-arm cohort, so unblinding is not applicable. However, only a limited number of individuals will have access to aggregated summary data prior to the final DBL for this cohort. To minimize any bias introduced into the analysis of the study results, the initial version of this SAP will be finalized and approved prior to initiating enrollment to this cohort.

# 6.15.2. Data Monitoring Committee/Assessment Committee

No data monitoring committee or assessment committee is planned for this cohort, as there are no preplanned interim analyses.

# 6.16. Planned Exploratory Analyses

# 6.16.1. Protocol-Defined Exploratory Endpoints

Protocol defined exploratory endpoints are described in Section 4.4 and analysis details are provided in the following sections.

#### 6.16.1.1. SARS-CoV-2 Viral Load

Change in viral load from baseline to Days 5, 7, and 11 will be assessed. An MMRM analysis will be employed to estimate the mean at each day, accounting for the effects of any missing data via the intrapatient covariance structure.

The AUC from Day 1 predose to Day 29 (AUC[0-D29]) will be calculated according to the linear trapezoidal rule using the measured SARS-CoV-2 viral load-time values above the lower limit of quantification. No imputations of missing data will be conducted. No AUC(0-D29) values will be calculated when Day 1 predose and/or Day 29 values are missing, or if there are more than 3 values missing in the profile.

The AUC from Day 1 predose to Day 11 (AUC[0-D11]) will be also calculated according to the linear trapezoidal rule using the measured SARS-CoV-2 viral load-time values above the lower limit of quantification. No imputations of missing data will be conducted. No AUC(0-D11) values will be calculated when Day 1 predose and/or Day 11 values are missing, or if more than 1 value is missing in the profile.

The AUC will be summarized and plotted for the cohort and listed.

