COVID-19 Symptoms	X	X	X	X	X	X	X	X	X	X	X				Day 1: assess prior to dosing The presence of absence of symptoms are collected from the participants or their parents/legal guardian.
Laboratory Tests and Sample Collections															
Hematology		X		X				X		X	X				Day 1: before treatment administration All other days: sample may occur at any time during the day Lilly-designated central laboratory

	Period I Screening	Period II Treatment Period											Period III Post- Treatment Follow-Up		
Study Day from Treatment Assignment		1	2, 3, 4	5	6	7	8, 9, 10	11	22	29	ED	Follow-up if hospital inpatient on Day 29	60	85	
Visit interval tolerance (days)		—	—	±1	—	+1	—	±2	±2	±3	±2	Every 7 days until discharge or Day 60	±4	±4	
Visit Detail		O	T,I	O,H	T,I	O,H	T,I	O,H	T,I	O,H	O,H		O,H	T,I	O = Outpatient clinic, H = Home Visit, T = Telephone, I = IT-Assisted Virtual Visit
Clinical Chemistry		X		X				X		X	X				Day 1: before treatment administration All other days: sample may occur at any time during the day Lilly-designated central laboratory
Documentation of positive SARS-CoV-2 viral infection	X														Sample for first positive test must be collected within 3 days prior to start of treatment administration. Local laboratory and/or Point-of- Care testing.
PD swab		X		X		X		X		X	X				Swab is taken from both nostrils. Day 1: swab before treatment administration. Methods include nasopharyngeal (preferred) or mid-turbinate. The same method of sample collection must be used per participant for the duration of the study. Switching methods is not allowed. Lilly-designated central laboratory

	Period I Screening	Period II Treatment Period											Period III Post- Treatment Follow-Up		
Study Day from Treatment Assignment		1	2, 3, 4	5	6	7	8, 9, 10	11	22	29	ED	Follow-up if hospital inpatient on Day 29	60	85	
Visit interval tolerance (days)		—	—	±1	—	+1	—	±2	±2	±3	±2	Every 7 days until discharge or Day 60	±4	±4	
Visit Detail		O	T,I	O,H	T,I	O,H	T,I	O,H	T,I	O,H	O,H		O,H	T,I	O = Outpatient clinic, H = Home Visit, T = Telephone, I = IT-Assisted Virtual Visit
Serum or Urine pregnancy (local)	X														Pregnancy tests prior to the first dose of investigational product for females if 
 aged ≥10 years <10 years at investigator’s discretion menarche is reached or there is reason to believe that the patient is sexually active. Local laboratory

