# 6.10. Efficacy Analyses

The analysis of the viral load lab results will utilize the following conventions:

For qualitative endpoints in the trial (viral clearance yes/no, time to viral clearance) the lab determination of "positive"/ "negative" will be used. SARS-CoV-2 clearance (yes/no) is defined as 2 consecutive negative tests for the SARS-CoV-2 virus. The date of viral clearance is defined as the earliest date of the 2 consecutive negative tests.

For quantitative endpoints in the trial (change from baseline, area under the response viral load curve [AUC]), the viral load will be derived based on cycle threshold (Ct) values with the following considerations:

Two Ct values will be provided on 2 different genes: N1 and N2. N1 will be used as the primary measure; N2 will only be used when the Ct value for N1 is not available.
Ct values range between 0 and 45.
Negative CoV-2 tests will be associated with a Ct value of 45.
The (log base 10) viral load will be calculated from the Ct value (45-Ct)/log 10, or (45-Ct)/3.321928.

□ A normalization step will also be applied. The viral load Ct value described in the previous steps will be subtracted by (RP Ct – 26.17), where RP Ct is a measure for the amount of material in the sample and 26.17 is a historical average value of RP Ct for this assay, used here to center the RP Ct values.

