### 6.16.2.6. Viral Load Plots

The 7th octile (87.5th percentile) for the observed viral load data will be plotted across Day 1, Day 5, Day 7, and Day 11. Additionally, the 4th (median), 5th (62.5th percentile), and 6th (75th percentile) octiles will be plotted separately.

The 4th, 5th, 6th, and 7th octile for viral load data adjusted for days from symptom onset at baseline will be plotted across Day 1, Day 5, Day 7, and Day 11. Viral load participant data will be adjusted by multiplying the participants number of days from symptom onset at baseline by 0.158 (estimated mean daily decrease in viral load) and then adding the result to all of the participants non-zero viral load measurements. Note, that if the observed viral load is zero, it will not be adjusted.

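### The viral-load AUC uses only values above the LLOQ, contradicting the SAP's own coding of negative swabs, and the AUC(0-D29) missing-value limit can exclude nobody

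*SAP*

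**What the plan says.** Section 6.10 of the SAP sets conventions for quantitative viral-load endpoints and lists the viral-load AUC among them. It states: "Negative CoV-2 tests will be associated with a Ct value of 45". Log10 viral load is then (45 - Ct)/3.321928. A normalization by the RP Ct value follows, and the section does not say whether it applies to negative tests.

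Section 6.16.2.6 (viral load plots) also regards zero as an observed result: "if the observed viral load is zero, it will not be adjusted".

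Section 6.16.1.1 defines AUC(0-D29) and AUC(0-D11) by the linear trapezoidal rule, each "using the measured SARS-CoV-2 viral load-time values above the lower limit of quantification", and rules out imputation. For the longer AUC it says: "No AUC(0-D29) values will be calculated when Day 1 predose and/or Day 29 values are missing". To this requirement on the two end swabs it adds a limit on the count: "or if there are more than 3 values missing in the profile". The shorter AUC requires Day 1 and Day 11 and is withheld "or if more than 1 value is missing in the profile".

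The Schedule of Activities in the protocol addendum (section 2.2.1, PD swab row) plans swabs on Days 1, 5, 7, 11 and 29, plus one at early discontinuation.

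**The concern.** There are two separate faults in the same section.

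First, section 6.10 makes a negative swab a usable value at the floor of the scale, while section 6.16.1.1 admits only values above the LLOQ. A load of 0 cannot meet that condition, so the AUC drops what section 6.10 supplies. The section does not say whether a dropped result counts as missing or is simply left out of the trapezoids. Neither the addendum nor this SAP gives an LLOQ value.

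The consequence falls on participants who clear the virus. If a below-LLOQ result counts as missing, anyone negative at Day 29 has no AUC(0-D29), and anyone negative at Day 11 has no AUC(0-D11). The summary is then restricted to participants still shedding at the end of the window, which is selection on the outcome being measured. If the result is merely left out, trailing negatives shorten the curve and lower the area. Under both readings, negatives between two positive swabs are bridged, which raises it. Two programmers following the text could report different participants and different values.

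Second, the limit on missing values for AUC(0-D29) looks like protection against sparse profiles but provides none.

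**Working it through.** **Value of a negative swab.** From SAP 6.10, Ct = 45 gives (45 - 45)/3.321928 = 0 before normalization. The constant reproduces: log2(10) = 3.321928. The conflict for negatives does not depend on the LLOQ value.

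**Effect on the area.** The swab days 1, 5, 7, 11 and 29 give intervals of 4, 2, 4 and 18 days. Each trapezoid is the interval length times the mean of its two end values. The log10 profiles below are assumptions, since the documents give none.

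| AUC | Assumed loads | Negatives entered as 0 | Negatives left out | Difference |
|---|---|---|---|---|
| 0-D29 | 6, 4, 2.5, 0, 0 | 20 + 6.5 + 5 + 0 = 31.5 | 20 + 6.5 = 26.5 | -16% |
| 0-D29 | 6, 5, 4, 3, 0 | 22 + 9 + 14 + 27 = 72 | 22 + 9 + 14 = 45 | -38% |
| 0-D29 | 7, 4, 0, 0, 1 | 22 + 4 + 0 + 9 = 35 | 22 + (4 + 1)/2 × 24 = 82 | +134% |
| 0-D11 | 7, 4, 0, 1 | 22 + 4 + 2 = 28 | 22 + (4 + 1)/2 × 6 = 37 | +32% |

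If below-LLOQ counts as missing, the first two profiles have no AUC(0-D29) because Day 29 is gone. The third still gives 82: both ends are present and only two values are missing.

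**The missing-value limit for AUC(0-D29).**
- Five scheduled swabs give 2^5 = 32 present/missing patterns.
- Days 1 and 29 are both present in 2^3 = 8 of them. These differ only at Days 5, 7 and 11, so at most 3 values are missing.
- More than 3 missing occurs in 6 of the 32 patterns, and all 6 already fail the Day 1/Day 29 requirement. The limit excludes 0 of the 8.
- More than 2 missing would exclude 1 of the 8, the profile with only Days 1 and 29.

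Cost of accepting that two-point profile, for assumed loads 7, 5, 4, 3, 1: the full area is 24 + 9 + 14 + 36 = 83. Days 1 and 29 alone give (7 + 1)/2 × 28 = 112, which is +35%.

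**The parallel limit for AUC(0-D11).** With Days 1 and 11 present there are 2^2 = 4 patterns. More than 1 missing excludes one of them, again the two-point profile. That limit works.

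**The case against.** The strongest reply is that section 6.10 says how loads are derived and section 6.16.1.1 says which loads enter the AUC, so the specific rule narrows the general one and the text is merely incomplete. That does not rescue it. Section 6.10 names the AUC among the endpoints its conventions serve, and applying the narrower rule as written still loses or distorts the AUC of participants who clear the virus.

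Several points stand as limits:

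- A negative is exactly 0 only before normalization. Read literally, the RP step moves it: an assumed RP Ct of 24.17 gives -0.60 and 28.17 gives +0.60. Exempting negatives is an inference from section 6.16.2.6 and has to be written down.
- An LLOQ may be given in main-study documents that were not available here.
- A participant positive through Day 11 and negative only at Day 29 has an unaffected AUC(0-D11). For 6, 5, 4, 3 it is 45 on any reading.
- Cutting the curve at the last positive is the less natural reading, given that a Day 29 value is required. The -16% and -38% figures depend on it; the natural alternative is no AUC at all.
- Nothing in the documents says how often these profiles occur. The +134% case needs negatives at Days 7 and 11 followed by a positive Day 29 swab.
- Removing the LLOQ condition also admits weak positives at face value. Section 6.10 already derives loads that way for change from baseline, with no LLOQ cut.
- The limit excludes nobody among scheduled swabs. Only counting an absent early-discontinuation swab as missing, for someone who attended Day 29, could reach four.

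**Conclusion.** Both parts hold. The LLOQ condition in section 6.16.1.1 contradicts the coding in section 6.10. As written, it either removes participants who are negative at the end of the window or gives them a shortened area, and it inflates the area where negatives lie between positives. The illustrated errors run from -38% to +134% for AUC(0-D29), with +32% in one AUC(0-D11) example. They rest on assumed profiles and show direction and scale, not expected frequency. The missing-value limit for AUC(0-D29) excludes 0 of 8 possible patterns, which follows from the swab schedule alone.

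The stakes are limited. The endpoint is exploratory, in a single arm with no comparison planned. The primary PK AUC and the mixed model for change in viral load do not use this rule. It should still be corrected, because the AUC is a protocol-listed endpoint and the rule as written gives a misleading summary.

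**What to change.** - **Section 6.16.1.1, both AUCs:** delete the LLOQ condition. State that every observed swab result enters by the section 6.10 convention, with negative tests at log10 load 0 and positive tests at their Ct-derived load, and that none of these counts as missing.
- **Section 6.16.1.1, AUC(0-D29):** change the limit to more than 2 values missing. Leave the AUC(0-D11) limit as it is.
- **Section 6.10:** add one sentence stating that the RP normalization does not apply to negative tests, so that they stay at 0 as section 6.16.2.6 assumes.

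The cost is two wording changes and one sentence, with no new data. Participants with swabs only at Days 1 and 29 lose their AUC(0-D29).
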